6.2.2. Exercise

Exercise is conducted at a stationary bike at moderate intensity defined as 50% of the heart rate reserve calculated using the formula of Tanaka et al.³⁴ ($HR = 50\% ((208 - 0.7 \cdot \text{age}) - HR_{\text{rest}}) + HR_{\text{rest}}$). The total duration of pedaling is 45 min or until clinical hypoglycemia (<3.0 mmol/l). If plasma glucose is below 3.9 mmol/l within 30 minutes before the exercise session, a 15 g dextrose is given orally every 15 minutes till glucose is above 3.9 mmol/l. These dextrose supplement will be accounted as a carbohydrate rescue in the analysis. Exercise session will start once the plasma glucose concentrations are above 3.9 mmol/l. However, subject will only bicycle for the remaining time of the exercise timeslot from 4.30 PM to 5.15 PM, i.e. if participants starts bicycling at 5:00 PM, they can exercise for 15 min or until clinical hypoglycemia (<3.0 mmol/l). Subjects will rate their exercise intensity using the Borg scale every 10 minutes.

6.2.3. Blood sampling procedures

A venous blood sample (0.5 ml) is collected every 10-30 min during closed-loop control and used for evaluation of CGM accuracy. We spin the sample and measure the plasma glucose value and the plasma lactate value using Yellow Spring Instruments 2900 STAT Plus (YSI). Immediately after the sample has been analyzed, we discard it. Additional measurements of plasma glucose and blood ketone (Freestyle Precision B-ketone, Abbott, Abbott Park, Illinois) may be performed at any time point if considered appropriate by the attending physician and/or if the participant is hypoglycemic or hyperglycemic (SOP_Dysglycemia). The total amount of blood to be drawn per participant does not exceed 120ml. The exact amount of blood drawn depends on the time spent in hypoglycemia and hyperglycemia (SOP_Dysglycemia).

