6.1. Pre-study

Screening visit: At the screening visit inclusion and exclusion criteria will be reviewed. The following data will be recorded: sex, age, race, pubertal stage (Tanner), diabetes duration, duration of insulin pump use, insulin pump settings (basal rates, insulin sensitivities, insulin:CHO ratios, insulin action time), total daily insulin dose (average of previous fourteen days), CGM usage, allergies, medical history, medications, height, weight, blood pressure, pulse rate, and hemoglobin A1c (HbA1c).

Randomization: The order of the two study periods will be determined by block randomization (using random blocks of 2 and 4). The randomization will be performed using the electronic capture system, REDCap. An allocation table generated by sealedenvelope.com will be uploaded to REDCap by a person not otherwise involved in the study. Using the randomization functionality of REDCap, the subjects will be randomized after ensuring that all criteria for participation have been met. The study is single-blinded and only the participants and their parents will be blinded to the intervention. Preparation, allocation and administration of the study drugs will be controlled and verified by two persons.

Continuous Glucose Monitoring Initiation: Two days before study start, one DexCom G6 CGM is inserted into the abdominal subcutaneous tissue of the study subject. Study subjects or their parents who are familiar with the procedure can do the insertion at home. However, the participants have to start the sensor up with the Dexcom receiver and not with the Dexcom app, since the transmitter only can be paired with one app. The pairing to our app is essential to run our closed-loop system. Participants who are inexperienced with the Dexcom CGM will get the sensor inserted at the research facility. No calibrations are needed for these CGMs.

Participant preparation: Prior to the first in-clinic study day, insulin pump settings (basal rate, insulin action time, insulin sensitivity factor, insulin:CHO ratio) are recorded as well as the insulin and CGM profiles for 3 days. The data are used for setting up the control algorithm.

Further, 24 hours before study start, the participant refrains from alcohol consumption and strenuous physical exercise. Participants are requested to consume a low-fat evening meal with 50% energy

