For every carbohydrate rescue during the study, 30 minutes of the time in range is allocated to time in hypoglycemia and will be accounted for in the primary analysis. A paired student's t-test will be used to compare the outcomes if data are normally distributed. Otherwise, a Wilcoxon Signed Rank test is be used. In order to account for missing values and adjusting for different factors, a repeated measurement ANOVA will be used with the outcome and adjusting factors as fixed effects and the intercept as a random effect. Bonferroni adjustments will be applied for non-specified outcomes.

Based on previous experience from this type of study we expect a very low drop-out rate, $< 10\%$.

Therefore, a maximum of 24 participants are needed for this project that includes phase 1 (N=4) and phase 2 (N=20).

If it turns out that deviations from the statistical plan described above are necessary, the Danish Health and Medicines Authority, the Regional Scientific Ethics Committee and the GCP-unit will be informed. The original statistical plan as well as the new strategy will be reported in the publication of study results.

10. Safety

For safety reasons, at least one study personnel will always be present during the clinical study.

10.1 Hypoglycemia management:

Hypoglycemia will be managed according to the standard operating procedures (SOP_Dysglycemia). A hypoglycemia episode is defined as one plasma glucose value < 3.0 mmol/l. In the event of a hypoglycemic episode, the attending physician will take immediate action to raise the blood glucose by providing the participant with oral carbohydrate. The treatment will be repeated if the hypoglycemia has not resolved within 15 minutes. Repeated YSI measurement will be performed every 5 minutes until BG is > 3.9 mg/dl (SOP_Dysglycemia).

If at any point during the study the participant experiences symptoms of hypoglycemia and requests oral carbohydrate, a blood sample for plasma glucose determination will be drawn. Irrespective of the plasma glucose value the participant will be treated with oral carbohydrate. However, repeated YSI measurements will only be measured if < 3.9 mmol/l.

If at any point during the study the participant experiences a severe hypoglycemic event, i.e. the participant is unable to take oral CHO, intravenous glucose will be administered via the sampling cannula and the study will be terminated.

10.2. Hyperglycemia management:

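### Unblinded staff may add plasma glucose samples at their judgement, and a low value leads to a rescue that adds 30 minutes to the primary outcome; the reason for each sample should be recorded and two sensitivity analyses prespecified

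*Combined protocol and SAP*

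**What the plan says.** Four provisions act together.

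- **Blinding (6.1, Randomization).** "The study is single-blinded and only the participants and their parents will be blinded to the intervention". The staff who run the visits are not blinded.
- **Sampling (6.2.3).** "A venous blood sample (0.5 ml) is collected every 10-30 min during closed-loop control", in both arms. Additional plasma glucose measurements "may be performed at any time point if considered appropriate by the attending physician". The same sentence also ties extra samples to hypo- or hyperglycemia and cites the dysglycemia SOP, which is listed in the appendix but not reproduced. The volume limit is "The total amount of blood to be drawn per participant does not exceed 120ml".
- **Rescue (10.1).** "A hypoglycemia episode is defined as one plasma glucose value < 3.0 mmol/l", and then "the attending physician will take immediate action to raise the blood glucose by providing the participant with oral carbohydrate". A participant with symptoms who asks for carbohydrate receives it whatever the plasma value. Section 6.2.2 adds a separate rule before exercise, and those supplements also count as rescues.
- **Analysis (9.2).** "For every carbohydrate rescue during the study, 30 minutes of the time in range is allocated to time in hypoglycemia", and this enters the primary analysis. The number of carbohydrate interventions is itself a secondary outcome (8.2.1.1).

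The plan does not distinguish rescues found on scheduled samples from those found on discretionary ones. It does not ask for sample counts by arm, and it plans no analysis of the primary outcome without the 30-minute reallocation.

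**The concern.** The primary outcome is labelled a CGM measure, but part of it depends on when blood is drawn. Apart from participant requests and the check before exercise, carbohydrate follows a plasma value, so a short low must coincide with a sample to become a rescue. The person who may order extra samples knows whether glucagon is running. If that knowledge alters how readily extra samples are taken, one arm could have more lows detected and more rescues scored at the same underlying glucose. This would be detection bias in the primary outcome and in the rescue count.

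The adult data in section 1.2 show why the rescue component deserves attention. Time in hypoglycemia differed by 3.75 - 3.63 = 0.12 points, while rescues differed by 1.42 - 0.8 = 0.62 over 33 hours. This does not show bias in the adult study, and section 1.2 does not say whether its percentages already include a reallocation. It does suggest that the rescue component could carry much of the primary result.

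**Working it through.** **Inputs.** Session length 26 h = 1560 min (6.2). Target difference 2.3 %-points, SD 3.0, two-sided 5%, power 90%, 20 completers, paired t-test (9.2). Reallocation 30 min per rescue (9.2). Scheduled samples of 0.5 ml every 10-30 min and a 120 ml limit per participant (6.2.3). Adult rescue means 0.8 and 1.42 over 33 h (1.2). The excess number of rescues, r, is not in the documents and is an assumption.

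**1. The plan's sample size.** Non-central t, paired, difference 2.3, SD of the within-person difference 3.0: power is 0.885 at n = 19 and 0.902 at n = 20. The stated 20 is reproduced.

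**2. Weight of one rescue.** 30/1560 = 1.92 %-points, and 1.92/2.3 = 84% of the target. This assumes that the full 30 minutes moves each time; the plan does not say how overlap with CGM time already below 3.9 mmol/l is handled.

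**3. Distance to significance.** The smallest significant mean difference is t(0.975, 19) × 3.0/√20 = 1.40 points, and 1.40/1.92 = 0.73 rescues per session.

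**4. Effect of unequal detection.** Shift = r × 1.92 points, carried through the same test at n = 20 with SD 3.0:

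| Excess rescues per session in one arm, r (assumed) | Shift (%-points) | Rejection rate with no true difference |
|---|---|---|
| 0.1 | 0.19 | 5.9% |
| 0.2 | 0.38 | 8.5% |
| 0.3 | 0.58 | 12.9% |
| 0.5 | 0.96 | 27.5% |

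Adding Poisson variance for the extra rescues lowers the last figure to 23.6%. If the excess fell in the dual-hormone arm and the true benefit were 2.3 points, power would drop from 90% to 84.6% at r = 0.1 and 47.4% at r = 0.5.

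**5. How plausible is r?** With random phase, a spell of L minutes meets a sample taken every d minutes with probability min(1, L/d). A 15-minute spell is met with probability 15/30 = 50% at 30-minute spacing and 15/20 = 75% at 20-minute spacing. For r = 0.3, extra sampling must catch every missed spell in one arm and none in the other. That needs 0.3/0.5 = 0.6 such spells per session at 30-minute spacing, or 0.3/0.25 = 1.2 at 20-minute spacing. Scaled to 26 h, the adult means are 0.8 × 26/33 = 0.63 and 1.42 × 26/33 = 1.12, a difference of 0.49. So r = 0.3 is about 60% of the whole adult difference, and r = 0.5 slightly exceeds it.

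**6. Does the volume limit prevent it?** At 0.5 ml per sample, 120 ml allows 240 samples over both sessions. A 30-minute schedule uses 2 × 52 = 104. The limit restricts the total but does not balance the arms.

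**The case against.** The strongest case on the other side is that little is left for discretionary samples to find. The 10-30 minute schedule applies to both arms, and section 6.2 makes the two visits identical apart from the control approach. Section 5.2 excludes people who report no symptoms below 3.0 mmol/l, and the blinded participant's request for carbohydrate is honoured whatever the value. An extra sample therefore adds a rescue only if the spell brings no request, falls between scheduled draws and would have resolved before the next one. Otherwise it only brings the rescue forward. The SOPs and the flow chart, not shown here, may also bind extra sampling to rules. All of this stands and limits the size. It does not remove the pathway, because section 6.2.3 names the physician's judgement as a ground in its own right.

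Three stronger readings are tempting and not supported:

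- **That detection differs between arms as 10-minute sampling differs from 30-minute sampling.** Those are the two ends of one common schedule. No figure shows what discretionary samples add to it.
- **That the bias favours dual-hormone control.** Staff might sample sooner when no glucagon is running. But earlier detection also means earlier treatment, which can shorten CGM time below 3.9 mmol/l and avoid a repeat treatment. The documents do not settle the direction.
- **That rescues found on discretionary samples should be left out of the primary analysis.** The carbohydrate raises glucose whichever sample prompted it, so leaving out the 30 minutes would make treated, plasma-confirmed lows look milder. If one arm were sampled more, that arm would lose more rescues and the bias could reverse. The deciding label would also be entered by unblinded staff.

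**Conclusion.** The concern holds as a possibility that the plan gives no means of checking. Every link is in the text: staff know the arm, may sample at their judgement, and a low value leads to a rescue worth 1.92 %-points. Neither size nor direction can be read from the documents. Over the assumed range of 0.1 to 0.5 excess rescues per session in one arm, the false-positive rate would rise from 5% to about 6-28%. The upper end needs an excess as large as the whole adult difference, so the lower part of the range is more credible. These rates assume SD 3.0, n = 20 and a full 30 minutes moved per rescue. This is a cheap improvement, not a flaw that undermines the design. If an SOP already fixes when extra samples are drawn, citing that rule in section 9.2 would largely answer the point.

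**What to change.** Leave treatment under section 10.1, the primary definition (all rescues counted) and outcome 8.2.1.1 unchanged. Add the following:

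1. In the eCRF, mark each plasma glucose sample at the time it is drawn as scheduled, required by a written rule, or discretionary. Record what triggered each rescue.
2. Report, by arm, the number of discretionary samples and the number of rescues they triggered.
3. In section 9.2, prespecify two sensitivity analyses of the primary outcome: (a) the 30-minute reallocation applied to all rescues except those triggered only by a discretionary sample; (b) CGM time below 3.9 mmol/l with no reallocation.

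If the primary result and both analyses agree, dependence on detection by unblinded staff is unlikely to matter. If they disagree, the counts by arm help to show why.

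The cost is one eCRF field with the rescue trigger, a few sentences in section 9.2 and a little more analysis, with no extra blood or staff. Analysis (a) leaves some treated lows uncompensated, so it is supportive only. The reason for a sample may not be recoverable later, so the field must be in place before the first visit.

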6.2.4. Glucose sensor procedures

Throughout the study day, sensor accuracy is evaluated every 30 minutes by comparing the sensor value with an YSI value. If the difference between a CGM value and a YSI value is more than 20%, the attending study personnel will assess whether to calibrate the sensor. Differences between CGM and YSI values are, however, expected two hours post-meal, post-snack or during exercise and in these periods, no calibrations will be performed even if the difference between CGM and YSI values exceeds the limits given above. If discrepancy persist even after calibration and restarting the sensors, the primary investigator will decide on whether to proceed or discontinue the study visit.

6.2.5. Procedures for device disconnections

CGM disconnection: If the CGM is disconnected, the application will immediately show red-coloured glucose values. If the CGM is disconnected for 15 min, an alarm will be raised from the smartphone and the attending study personnel will troubleshoot the system.

Pump disconnection: If the insulin and/or the glucagon pump do not respond to the smartphone for 15 min, an alarm will be raised from the smartphone and the attending study personnel will troubleshoot the system.

Smartphone disconnection: If the smartphone application crashes (an unexpected error forcing the application to stop), the application will automatically restart. An alarm will be raised, and a tool bar will appear on the button of the screen, indicating the app crash. The study personnel will immediately restart the system.

7. The Dual-Hormone Closed-Loop System: Medical Devices and Medication

The dual-hormone system consists of several components, i.e. two Dana-RS insulin pumps (one containing insulin and one containing glucagon or saline), one DexCom G6 CGM sensor, and one Samsung Galaxy A5 2017 Android phone operating the control algorithm for the closed-loop glucose control (Figure 6 and for more details see the Investigator’s brochure).

Figure 6: Devices for our closed-loop system: 2 x Dana-RS insulin pump, 1 x DexCom G6 CGM, and Samsung Galaxy A5 2017 Android phone operating the control algorithm for the closed-loop glucose control.

7.1. Medical devices

7.1.1. Insulin Pump, Dana Diabecare RS® insulin pump

For insulin infusion we use a CE-marked Dana Diabecare RS insulin pump (SOOIL Development, Seoul, Korea). The product is commercially available by prescription and is indicated for insulin infusion in participants with T1D (see instruction for use). The same pump is used throughout the study, however, consumables including CE-marked cartridges and infusion sets (Dana Inset II,

Unomedical, ConvaTec) are discarded at the end of each study. Pump and infusion set are depicted in figure 1. All investigators are trained and experienced in the use of the Dana Diabecare RS insulin pump. For this study all device handling is managed by the investigators and accordingly no subject training is needed. The investigators will insert the pump according to manufacturer's instructions.

The pump has a mechanical dosing resolution of 0.01 unit. The reservoirs can hold 300 units (3 ml) of insulin. The pump will be slave to the control algorithm controlled by the Samsung Galaxy A5 2017 Android phone.

7.1.2. Glucagon Pump, Dana Diabecare RS® insulin pump

For glucagon infusion, we use the CE-marked Dana Diabecare RS insulin pump (SOOIL Development, Seoul, Korea). The same pump is used throughout the study, however, consumables including CE-marked cartridge and infusion set (Dana Inset II, Unomedical, ConvaTec) are discarded at the end of each study. Pump and infusion set are depicted in figure 1. All investigators are trained and experienced in the use of the Dana Diabecare RS insulin pump. For this study all device handling is managed by the investigators and accordingly no subject training is needed. The investigators will insert the pump according to manufacturer's instructions.

As mentioned above, the product is only CE-marked for insulin infusion and the indications do not include glucagon infusion (see instruction for use). However, we have performed a similar study on adults. Other dual-hormone studies have used GlucaGen® in other insulin pumps but with similar cartridge and infusion sets as we will use in this study. In the first part of the adult study, occlusion issues were present but after shifting to Unomedical infusion sets, we have not experienced any infusion set failure. None of the other studies using Unomedical infusion sets have reported malfunctions regarding the pump infusion of GlucaGen®³⁵⁻⁴⁰.

On the placebo day, the pump will function as a “dummy” pump and will not infuse anything. The pump will therefore not be controlled by the control algorithm. However, the pump is filled with isotonic saline in order to uphold the blinding and to avoid alarms indicating empty cartridge from the pump. Still, the solution will not be infused to the participant.

7.1.3. Continuous Glucose Monitoring, DexCom G6®CGM

For glucose monitoring we use CE-marked DexCom G6 (DexCom, San Diego, California) CGMs (figure 7). The product is commercially available by prescription and indicated for participants with T1D (see instruction for use). All investigators are trained and experienced in the use of the DexCom G6 continuous glucose monitor. For this study all device handling is managed by the investigators and accordingly no subject training is needed. The investigators will insert the continuous glucose monitoring device according to manufacturer's instructions.

[figure not shown]

Figure 7: DexCom G6 continuous glucose monitoring system with (1) inserter, (2) sensor and transmitter, and (3) display device

7.1.4. Control algorithm

The control algorithm is not CE-marked. It is constructed by use of MPC theory and consists of two main components: an insulin controller and a glucagon controller. The system can operate with either the insulin controller alone or with both controllers activated simultaneously. When only the insulin controller component is activated, the system exerts single-hormone control. When both the insulin and the glucagon controller components are activated, the system exerts dual-hormone control. However, even with both controllers activated, the system does not deliver insulin and glucagon simultaneously. The MPC algorithm calculates the appropriate doses of insulin and glucagon to be delivered by the pumps (SOP_DiaCon_algorithm).

Software/algorithms developed by DiaCon are updated since the adult study and comprise the following:

7.1.5 Dexcom CGM communication:

DIACON_AP_ANDROID_CGM_DEXCOM VERSION 2.0

Dana RS insulin pump communication:

DIACON_AP_INSULIN_ANDROID_PUMP_DANARS_VERSION 2.0

Dana RS glucagon pump communication:

DIACON_AP_GLUCAGON_ANDROID_PUMP_DANARS_VERSION 2.0

Model Predictive Control Algorithms and Logics

DIACON_AP_MPC_CGM_INSULINGLUCAGON_PUMP VERSION 2.0

Grahical User Interface (GUI)

DIACON_AP_GUI_ANDROID VERSION 2.0

The software/algorithms developed by DiaCon will be archived and updates/modifications will be given a new version number. Each major version number will be associated with a major clinical trial. If minor modifications are made, they will be given a number such as VERSION 2.1 and a logbook will explain the changes made. All software used in clinical trials will be tested extensively by simulation in advance, go through a DiaCon review procedure, and be archived. The main changes introduced in version 2.0 increased the safety of the system. They are the following:

- 1) Basal rate upper limit: The maximum insulin delivery is set to 2.5 times the basal rate.
- 2) Boluses: Boluses are only allowed within 2 hours after a meal. The insulin bolus is limited to 1.3 times the bolus computed using the participant specific insulin-to-carbohydrate ratio (ICR). The total allowed dose is given by the formula: $u_{\max, \text{bol}} = 1.3 * (\text{gram carbohydrate content in meal}) / \text{ICR}$.

If a second meal is given within 2 hours after a meal, the timer is reset and the new maximum bolus is added to the current maximum bolus.

- 3) Glucagon: The glucagon is always administered as boluses. The glucagon limit has been raised from 200 to 300 μg over 2 hours. The glucagon threshold has been raised to 4.5 mmol/L instead of 4.0 mmol/L.
- 4) Pump: An alarm sounds from the smartphone if the system cannot connect to the pump.
- 5) Sensor: An alarm sounds from the smartphone if the system cannot connect to sensor.

